9.3 Sample Size and Power Considerations

A total sample size of approximately 350 subjects (175 in the experimental arm [luspatercept (ACE-536)], 175 in the control arm [epoetin alfa]) will have 90% power to detect the difference between a RBC-TI (for 12 weeks associated with a concurrent hemoglobin increase) response rate of 36% in the experimental arm (luspatercept [ACE-536]) and a response rate of 20% in the control arm (epoetin alfa), with the first interim analysis on futility only when about 105 subjects have completed 24 weeks of treatment, or discontinued before reaching 24 weeks of treatment (30% information for primary endpoint). The Lan-DeMets (O'Brien-Fleming) spending function will

³ Instrument-dependent.

be used as the futility boundary. The sample size calculation is based on one-sided alpha of 0.025, test statistics on odds ratio of proportions using the EAST[®] Version 6.4 software system.

A second interim analysis to test the superiority of the luspatercept arm does not alter the above sample size calculation. The study power remains at 90% for the final analysis with 350 subjects and the Lan-DeMets spending function of the O'Brien-Fleming type will be used to control the overall one-sided Type I error rate at 0.025.

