9.4 Randomization and Stratification

Subjects will be randomized to receive luspatercept or epoetin alfa at a 1:1 ratio.

Randomization will be accomplished by an IRT to ensure timely registration and randomization. A stratified randomization schedule will be implemented. Randomization will be stratified by baseline RBC transfusion burden, RS status, and endogenous serum erythropoietin (sEPO) level at baseline:

- RBC transfusion burden at baseline
 - < 4 pRBC units/8 weeks
 - ≥ 4 pRBC units/8 weeks
- Ring sideroblast (RS) status at baseline (with RS+ defined as ring sideroblasts ≥ 15% of erythroid precursors in bone marrow or ≥ 5% (but < 15%) if SF3B1 mutation is present).
 - RS+
 - RS-
- Endogenous Serum Erythropoietin (sEPO) level at baseline.
 - ≤ 200 U/L
 - > 200 U/L

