9.7.2 Secondary Efficacy Analyses

The secondary efficacy endpoints will be analyzed and reported at the time of the analysis of the primary efficacy endpoints.

Secondary endpoints will be analyzed descriptively, unless otherwise specified, and will be based on the ITT population. Kaplan-Meier methods will be used to estimate curves for time to event secondary variables. Count, percentages, and 95% confidence interval will be used to describe categorical secondary variables.

Gate-keeping method will be used to control the overall Type I error rate for the following secondary endpoints in the order of:

- HI-E response (Week 1 to 24)
- RBC-TI for 24 weeks (Week 1 to 24)
- RBC-TI ≥ 12 weeks (Week 1 to 24)

After the result from the primary efficacy endpoint shows statistical significance, RBC-TI for 24 weeks in Week 1 to 24 will be tested for significance at the one-sided significance level of 0.021 only if both primary endpoint and HI-E response in Week 1 to 24 are significant. RBC-TI ≥ 12 weeks in Week 1 to 24 will be tested for significance at the one-sided significance level of

0.021 only if the results for primary endpoint, HI-E in Week 1 to 24, and RBC-TI for 24 weeks in Week 1 to 24 are all significant. The testing procedure above will be implemented strictly in order to control the overall one-sided Type I error rate of 0.025 due to multiplicity.

Other secondary endpoints will be analyzed without employing methods for controlling the type one error rate. Any statistically significant treatment effect on these secondary endpoints cannot be interpreted as confirmatory, but rather informative.

RBC transfusion independence (RBC-TI) for 24 weeks is defined as the absence of any RBC transfusion from Week 1 to the end of Week 24. Subjects discontinued from the Treatment Phase prior to finishing Week 24 will be counted as non-responders.

Mean hemoglobin change over 24 weeks is defined as the mean hemoglobin change over the 24-week period of Week 1 through Week 24 compared to baseline

Hematologic improvement – erythroid response (HI-E) per IWG (Cheson, 2006) is defined as proportion of subjects meeting HI-E criteria sustained over any consecutive 56-day period over the first 24 weeks from Week 1. Subjects discontinued from the Treatment Period without achieving HI-E will be counted as non-responders.

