9.10 Other Topics

9.10.1 Health-related Quality-of-life Assessment

The effect of luspatercept and epoetin alfa on patients' HRQoL based on EORTC QLQ-C30, FACT-An, QUALMS-P and the Patient Treatment Satisfaction Survey will be assessed. The intent is to summarize the descriptive statistics of observed score at each visit and change from baseline at each post-baseline visit for all domains of the QLQ-C30 and FACT-An, QUALMS-P for each treatment group. Within-treatment and between-treatment differences will be examined using a 1-sample, 2-sided t-test and a pooled 2-sample, 2-sided t-test, respectively. However, these t-tests will be descriptive (ie, non-inferential) in nature.

In addition, the least square (LS) mean (95% confidence interval [CI] and p-value) for change from baseline at each post-baseline visit for all domains within each treatment group, and the difference in the LS means (95% CI, p-value) between treatment groups at each post-baseline visit, will be

estimated using the analysis of covariance (ANCOVA) model adjusting for baseline domain scores and stratification factors (ie, transfusion burden, RS status and sEPO level) where appropriate. Various schemes will be assessed for missing data imputation. Full details will be included in an HRQoL SAP.

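### Section 9.7.2 specifies no between-arm estimate adjusted for baseline and stratification factors for mean hemoglobin change or RBC units transfused, although HRQoL, also outside the gate, has one

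*Combined protocol and SAP*

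**What the plan says.** Protocol Section 9.7.2 sets the default: "Secondary endpoints will be analyzed descriptively, unless otherwise specified, and will be based on the ITT population". It then assigns Kaplan-Meier estimation to time-to-event variables, and counts, percentages and 95% confidence intervals to categorical ones. It assigns nothing to continuous or count variables.

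Two secondary endpoints in Table 2 are of that kind, and Section 9.7.2 gives each a definition only:

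- **Hemoglobin.** "Mean hemoglobin change over 24 weeks is defined as the mean hemoglobin change over the" 24-week period, relative to baseline. The baseline value is subtracted but is not a covariate.
- **RBC transfusion burden.** The total number of units given in the first 24 weeks of treatment, with no baseline term.

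Only HI-E, RBC-TI for 24 weeks and RBC-TI of at least 12 weeks enter the gate-keeping. Other secondary results are declared informative rather than confirmatory, and full details are left to the SAP.

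Elsewhere the protocol does adjust. Section 9.7.1 uses a CMH test for the primary endpoint with the randomization factors as strata. Section 9.10.1 analyses HRQoL change with an ANCOVA "model adjusting for baseline domain scores and stratification factors", naming transfusion burden, RS status and sEPO level.

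**The concern.** The secondary objective is comparative: efficacy of luspatercept against epoetin alfa. For these two endpoints a reader of Section 9.7.2 cannot tell what the comparison will be. If the default is applied as it stands, the result is arm summaries that use neither the three factors nor, for RBC units, the baseline value.

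Section 1.3.2.2 justifies the factors by their expected influence on the study endpoints, and expects transfusion independence to be related to baseline transfusion burden. Stratifying on prognostic factors and then leaving them out of the analysis generally gives standard errors that are too large. An unadjusted comparison also keeps any chance baseline difference that the two-level strata do not remove. Baseline units may run from 2 to 6 per 8 weeks (Section 4.2), a threefold range, whereas the stratum only separates fewer than 4 from 4 or more.

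The trial is open-label, which is a further reason to fix model and covariates in advance. What is at stake is the precision and interpretability of two supportive estimates, not the primary conclusion.

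**Working it through.** **1. The plan's own figure.** The protocol gives no power, SD or precision for either endpoint. Its one sample-size statement concerns the primary endpoint: "A total sample size of approximately 350 subjects" "will have 90% power to detect the difference between a RBC-TI" response of 36% against 20%, and "The sample size calculation is based on one-sided alpha of 0.025, test statistics on odds ratio of proportions". With 175 per arm:

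- odds ratio = (0.36/0.64)/(0.20/0.80) = 2.25; ln 2.25 = 0.811
- v = 1/(0.36 × 0.64) + 1/(0.20 × 0.80) = 4.34 + 6.25 = 10.59; SE = √(10.59/175) = 0.246
- power = Φ(0.811/0.246 − 1.960) = 90.9%

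The stated 90% reproduces, and nothing in it depends on how these two endpoints are analysed.

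**2. Formula for hemoglobin.** Let ρ be the correlation between baseline and on-treatment mean hemoglobin, and k the baseline SD divided by the on-treatment SD. In units of the on-treatment variance:

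- change-score variance = k² + 1 − 2ρk
- ANCOVA variance (large sample) = 1 − ρ²
- relative reduction = 1 − (1 − ρ²)/(k² + 1 − 2ρk) = (k − ρ)²/(k² + 1 − 2ρk)

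The numerator is a square, so in large samples ANCOVA is never less precise than the change score. The gain is zero when k = ρ. With k = 1 the reduction is (1 − ρ)/2.

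**3. Inputs.** The documents state neither ρ nor k. Both are assumed here: ρ from 0.3 to 0.6, k from 0.5 to 1.25.

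**4. Equal SDs (k = 1).**

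| ρ | ANCOVA / change-score variance | Interval narrower by | 350 subjects act like |
|---|---|---|---|
| 0.3 | 0.65 | 1 − √0.65 = 19% | 350/0.65 = 538 |
| 0.5 | 0.75 | 1 − √0.75 = 13% | 350/0.75 = 467 |
| 0.6 | 0.80 | 1 − √0.80 = 11% | 350/0.80 = 438 |

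At ρ = 0.8 the variance reduction is 10%.

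**5. Unequal SDs.** Variance reduction:

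| k | ρ = 0.3 | ρ = 0.5 | ρ = 0.6 |
|---|---|---|---|
| 0.5 | 4% | 0% | 2% |
| 0.75 | 18% | 8% | 3% |
| 1.25 | 50% | 43% | 40% |

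**6. Adding the three factors.** If they explain a further assumed 2% to 10% of the residual variance, the reduction with equal SDs is 1 − (1 − ρ²)(1 − R²)/(2 − 2ρ). That is 36% to 42% at ρ = 0.3 and 22% to 28% at ρ = 0.6.

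**7. RBC units.** The documents give no distribution for the total, so no gain is computed. The structural points are that the definition has no baseline term and no term for length of observation. Under Section 6.4.1, transfusion collection runs to 8 weeks after the last dose or the EOT Visit, whichever is later. A subject who stops early can therefore be observed for less than 24 weeks and show a low total for that reason alone.

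**The case against.** The strongest reply is that the protocol does not rule out an adjusted comparison. The default carries an exception clause, Section 9.7.2 foresees significance statements on the other secondary endpoints, and full details go to the SAP, whose separate text is not in the document reviewed. In Section 9.10.1 between-arm t-tests are themselves called descriptive, so the word may describe inferential status rather than exclude an estimate. This stands as a limit. A reader might infer that the two endpoints will be analysed only descriptively; the documents show only that Section 9.7.2 states no adjusted estimate.

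A reader might also infer that baseline hemoglobin is ignored. It is not: it enters by subtraction, and under randomization the change score is unbiased. The issue is efficiency and chance imbalance.

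A third tempting reading is that the plan loses 20% to 35% of the attainable variance reduction. Those percentages are shares of the change-score variance, a different quantity, and need equal SDs with ρ between 0.6 and 0.3. Section 4.2 requires hemoglobin below 11.0 g/dL after the last transfusion, while on treatment a mixture of responders and non-responders is expected. That may make k less than 1 and the gain small.

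Finally, both endpoints are outside the gate, and stratified randomization already limits imbalance in transfusion burden. That keeps the point minor. It does not explain why HRQoL, with the same status, is adjusted. The subgroup analyses by stratification factor in Section 9.10.7 do not supply an overall adjusted estimate.

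**Conclusion.** The point holds as a minor, nearly free improvement. Section 9.7.2 leaves mean hemoglobin change and RBC units without a between-arm estimate adjusted for baseline and the three factors, in contrast to Section 9.10.1.

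For hemoglobin the direction of the gain does not depend on the assumptions, but its size does. At equal SDs and an assumed correlation of 0.3 to 0.6, the variance reduction is 20% to 35%. Over assumed SD ratios of 0.5 to 1.25 it is about 0% to 50%. No single figure should be quoted as the loss. For RBC units the effect is unquantified, and the missing baseline and follow-up-time terms are the substance. The material supports no claim of bias, inflated type I error or reduced primary power.

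**What to change.** In Section 9.7.2 and the SAP:

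- **Mean hemoglobin change:** ANCOVA with treatment, baseline hemoglobin and the three randomization factors, reporting the adjusted mean difference with its 95% CI.
- **RBC units:** a count model, for example negative binomial, with treatment, baseline units, RS status and sEPO stratum, and log follow-up time as an offset, reporting the rate ratio with its 95% CI. Baseline units replace the transfusion-burden stratum, which is the same variable in two classes. State the window that defines units and follow-up time. The offset corrects for length of observation, not for discontinuation related to outcome.
- State that both remain outside the gate and non-confirmatory. If an efficiency gain is cited, give it as a range with the assumed correlation and SD ratio.

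If the SAP already contains such models, a cross-reference from Section 9.7.2 is enough. The cost is a few lines of text and two models. The covariates and transfusion dates are already collected, and sample size, alpha levels and testing order do not change.

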Primary	Red blood cell transfusion independence (RBC-TI) for 12 weeks (84 days) with a mean hemoglobin increase ≥ 1.5 g/dL	Proportion of subjects who are RBC transfusion-free for any 12-week period associated with a concurrent mean hemoglobin increase ≥ 1.5 g/dL compared to baseline	Week 1 through Week 24
Secondary	Red blood cell transfusion independence (RBC-TI) for 24 weeks	Proportion of subjects who are RBC transfusion-free from Week 1 through Week 24	Week 1 through Week 24
	Mean hemoglobin change over 24 weeks	Mean hemoglobin change over the 24-week period of Week 1 through Week 24 compared to baseline	Week 1 through Week 24
	Hematologic improvement – erythroid response (HI-E) per IWG (Cheson, 2006)	Proportion of subjects achieving HI-E over any consecutive 56-day period	Week 1 through Week 24
	Time to HI-E	Time from first dose to first onset of achieving HI-E	Week 1 through Week 24
	RBC-TI for ≥ 12 weeks (84 days)	Proportion of subjects who are RBC transfusion-free over a consecutive 84-day period	Week 1 through Week 24
	Duration of RBC-TI ≥ 12 weeks (84 days)	Maximum duration of RBC transfusion independence for subjects who achieve RBC-TI ≥ 84 days	Week 1 through End of Treatment
	Time to RBC-TI ≥ 12 weeks (84 days)	Time from first dose to first onset of transfusion independence ≥ 84 days	Week 1 through Week 24
	Time to first RBC transfusion	Time from first dose to first transfusion on treatment	Week 1 through End of Treatment
	RBC transfusion burden on treatment	Total number of RBC units transfused on treatment	Week 1 through Week 24
	RBC-TI for ≥ 56 days (8 weeks)	Proportion of subjects who are RBC transfusion-free over a consecutive 56-day period	Week 1 through Week 24
	RBC-TI for a consecutive 24-week period	Proportion of subjects who are RBC transfusion-free for a consecutive 24-week period in the first 48 weeks from first dose	Week 1 through Week 48
	Health-related quality-of-life (HRQoL)	Evaluation of EORTC QLQ-C30 score and FACT-An	Screening through Week 24
	Safety	Type, frequency, severity of AEs and relationship of AEs to luspatercept/epoetin alfa	Screening through 42 days post last dose; Randomization through Week 48

Table 2: Study Endpoints

Endpoint	Name	Description	Timeframe
Secondary (continued)	PK parameters	Serum luspatercept concentrations and PK parameters	Randomization through 1 year post first dose
	Antidrug antibodies (ADA)	Frequency of antidrug antibodies	Randomization through 1 year post first dose

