Time to HI-E will be summarized only for subjects who achieve HI-E response. It is defined as time from Week 1 to first onset of achieving HI-E. It will be summarized only for subjects who achieve HI-E within the first 24 weeks from Week 1.

RBC-TI for ≥ 12 weeks (84 days) is defined as the proportion of subjects achieving RBC-TI for ≥ 84 days during any consecutive 84-day period from Week 1 through Week 24.

Duration of RBC-TI ≥ 12 weeks (84 days) is defined as the longest RBC-TI period for subjects who achieve RBC-TI ≥ 12 weeks from Week 1 through Week 24. Subjects who maintain RBC-TI through the end of the Treatment Period or at the time of analysis will be censored at the date of treatment discontinuation, date of analysis or death, whichever occurs first.

Time to RBC-TI ≥ 12 weeks (84 days) will be summarized only for subjects who achieve RBC-TI ≥ 84 days from Week 1 through Week 24. It is defined as the time between Week 1 and the date onset of TI is first observed (ie, Day 1 of 84 days without any RBC transfusions).

Time to first RBC transfusion is defined as time from Week 1 to first RBC transfusion on treatment. Subjects who maintain RBC-TI through the end of the Treatment Period or time of analysis will be censored at the date of treatment discontinuation/time of analysis or death, whichever occurs first.

RBC transfusion burden on treatment is defined as total number of pRBC units transfused within the first 24 weeks of treatment since Week 1.

RBC-TI for ≥ 56 days (8 weeks) is defined as the proportion of subjects achieving RBC-TI for ≥ 56 days during any consecutive 56-day period from Week 1 through Week 24.

RBC-TI for a consecutive 24-week period is defined as the proportion of subjects achieving RBC-TI for ≥ 168 days during any consecutive 168-day period from Week 1 through Week 48.

Progression to AML: time to AML progression is defined as the time between randomization and first diagnosis of AML as per WHO classification of $\geq 20\%$ blasts in peripheral blood or bone

marrow. Subjects with diagnosis of AML will be considered to have had an event. Subjects who have not progressed to AML at the time of analysis will be censored at the last assessment date which does not indicate progression to AML.

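### Time to HI-E and time to RBC-TI of at least 12 weeks are summarised in responders only, so side-by-side arm figures do not show which drug works sooner and could rank the arms wrongly

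*Combined protocol and SAP*

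**What the plan says.** Section 9.7.2 of the protocol limits the analysis set for two secondary endpoints.

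- **Time to HI-E:** "Time to HI-E will be summarized only for subjects who achieve HI-E response", and again, "It will be summarized only for subjects who achieve HI-E within the first 24 weeks from Week 1".
- **Time to RBC-TI of at least 12 weeks:** it "will be summarized only for subjects who achieve RBC-TI" of at least 84 days from Week 1 through Week 24. Onset is taken as "Day 1 of 84 days without any RBC transfusions".

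The same section sets general rules for secondary endpoints: "Secondary endpoints will be analyzed descriptively, unless otherwise specified, and will be based on the ITT population"; and "Kaplan-Meier methods will be used to estimate curves for time to event secondary variables". It gives censoring rules for duration of RBC-TI and for time to first transfusion, but none for these two times to onset.

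Table 2 in Section 2 defines the first endpoint as "Time from first dose to first onset of achieving HI-E" and does not mention responders. The entry for duration of RBC-TI in the same table does limit itself to those who achieve it. The secondary efficacy objective in Table 1 is worded as a comparison of luspatercept with epoetin alfa.

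Neither endpoint is in the gatekeeping sequence. For endpoints outside it the plan says: "Any statistically significant treatment effect on these secondary endpoints cannot be interpreted as confirmatory, but rather informative".

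**The concern.** Whether a subject responds is an outcome of treatment. Restricting a time-to-onset summary to responders compares two groups selected by that outcome, and randomization no longer makes them alike. A drug that helps more people may do so by adding responders who would not have responded on the other arm. If those added responders respond later than the rest, they lengthen that arm's responder-only median, even though nobody in the arm responds later than they otherwise would have.

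What is at stake is how a descriptive result is read. Under an objective worded as a comparison, responder-only times shown for each arm invite the conclusion that the arm with the shorter median works sooner. The summary cannot support that conclusion.

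**Working it through.** **Inputs from the plan.** Primary-endpoint response rates of 36% (luspatercept) and 20% (epoetin alfa), 175 per arm, one-sided alpha 0.025, 90% power (Section 9.3). The plan gives no assumed rate for HI-E or RBC-TI of at least 12 weeks, and no onset-time distribution.

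**The plan's own figure.** Odds ratio = (0.36/0.64)/(0.20/0.80) = 2.25, with log 0.811. Standard error = √[1/(175×0.36×0.64) + 1/(175×0.20×0.80)] = 0.246. Power = Φ(0.811/0.246 − 1.96) = 90.9%. A test on the difference in proportions gives 91.9%. The stated 90% is reproduced, and no stated figure is in dispute.

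**Last possible onset.** The window is 24×7 = 168 days. RBC-TI needs 84 days, so onset is no later than Day 168 − 84 + 1 = 85. HI-E needs 56 days, so no later than Day 168 − 56 + 1 = 113.

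**Illustration (onset times assumed).** Both arms have 20% early responders with mean onset at week 3. Luspatercept has a further 16% with mean onset at week w. Luspatercept's true cumulative response is then never below epoetin alfa's.

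- Responder-only mean, luspatercept: (20×3 + 16×w)/36. Epoetin alfa: 3.0.
- Mean weeks without response up to week 12, all randomized, luspatercept: 0.20×3 + 0.16×w + 0.64×12. Epoetin alfa: 0.20×3 + 0.80×12 = 10.2.

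For example, at w = 9: (60 + 144)/36 = 5.7 weeks among responders, and 0.6 + 1.44 + 7.68 = 9.7 weeks among all randomized.

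The simulation used 10,000 trials for each w, with normal onset times (SD 1.5 weeks) held within weeks 0 to 12. That range is possible for both endpoints.

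| Late onset w (week) | Responder-only mean, L vs E | Simulated responder-only median, L vs E | Luspatercept median longer | Weeks without response, L vs E | All-randomized order right |
|---|---|---|---|---|---|
| 9 | 5.7 vs 3.0 | 5.1 vs 3.0 | 99.8% | 9.7 vs 10.2 | 89% |
| 6 | 4.3 vs 3.0 | 4.3 vs 3.0 | 99.5% | 9.2 vs 10.2 | 99% |
| 4 | 3.4 vs 3.0 | 3.4 vs 3.0 | 86% | 8.9 vs 10.2 | 99.9% |
| 3 (no late group) | 3.0 vs 3.0 | 3.0 vs 3.0 | 51% | 8.8 vs 10.2 | 100% (rounded) |

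**Varying the luspatercept rate.** With w = 9, the responder-only mean is (20×3 + (p − 20)×9)/p for a luspatercept rate of p%. This gives 4.2, 5.0, 5.7, 6.3 and 7.0 weeks at p = 25, 30, 36, 45 and 60, against 3.0 on epoetin alfa throughout. Under this pattern, the larger the true benefit, the slower luspatercept looks.

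**The other direction.** If the added responders were earlier than the rest, say w = 2, the mean would be (60 + 32)/36 = 2.6 weeks and the order would be right. Reversal needs added responders who are later.

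**The case against.** The strongest reply is that no comparison of speed is planned. Section 9.7.2 says the times are summarised and names no test, hazard ratio or between-arm estimate for them. Time to response among responders is a valid answer to a narrower question: given a response, when did it come? The ITT response rates for HI-E and RBC-TI of at least 12 weeks are formally tested in sequence, and time to first transfusion has no responder restriction. A careful reader would see the higher response rate next to the longer median. The general ITT rule also carries an exception for endpoints specified otherwise, and Table 2 can be read as leaving the analysis set to Section 9.7.2. The sections do not flatly contradict each other. Section 9.7.2 also defers full details to the SAP.

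Much of this stands, and it is why the point is small. It does not remove the point. Neither the response rates nor time to first transfusion shows time to onset of response. The deferral does not reopen the analysis set either, because the restriction is already written as exclusive and no SAP text in the document provided changes it.

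Two stronger readings are tempting. A reader might infer that stepwise titration makes late response likely on luspatercept, so that reversal is to be expected. The documents do not support this. Sections 7.2.1.2 and 7.2.2.2 allow dose increases from W7D1 in both arms, and Section 1.2.2 reports HI-E on luspatercept within the first 3 months without comparing onset with epoetin alfa. A reader might also infer that an invalid between-arm test is planned. None is.

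**Conclusion.** The point holds as a minor one. The responder-only summaries of time to HI-E and time to RBC-TI of at least 12 weeks do not show which drug works sooner, and they can put the arms in the wrong order when the arms' responders differ in onset timing.

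The simulated error rates, from 51% with no late group to 99.8% with late onset at week 9, describe one assumed pattern and do not forecast this trial. They rest on primary-endpoint rates borrowed for two other endpoints, on equal early response in both arms, and on onset times that the documents do not give.

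Type I error, power and the primary conclusion are unaffected.

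**What to change.** In Section 9.7.2, add as the between-arm display the cumulative incidence of first HI-E and of first RBC-TI of at least 12 weeks, by arm, in the ITT population:

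- Keep non-responders at risk to the last possible onset, about Day 113 for HI-E and Day 85 for RBC-TI.
- Treat death or treatment discontinuation without response as competing events.
- Keep the responder-only summaries as supportive, labelled as a description of responders and not a comparison of arms.
- Align the wording in Table 2, the general rules and the two endpoint definitions.

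The cost is one extra figure or table per endpoint. It needs no new data and no change to alpha, sample size or the testing sequence.
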